# 11.3 Site monitoring

Before study initiation, at a site initiation visit or at an investigator's meeting, a Novartis representative will review the protocol and data capture requirements (i.e., eCRFs)

with the investigators and their staff. During the study, Novartis employs several methods of ensuring protocol and GCP compliance and the quality/integrity of the sites' data. The field monitor will visit the site to check the completeness of participant records, the accuracy of data capture / data entry, the adherence to the protocol and to Good Clinical Practice, the progress of enrollment, and to ensure that study treatment is being stored, dispensed, and accounted for according to specifications. Key study personnel must be available to assist the field monitor during these visits. Continuous remote monitoring of each site's data may be performed by a centralized Novartis/CRA organization. Additionally, a central analytics organization may analyze data & identify risks & trends for site operational parameters, and provide reports to Novartis clinical teams to assist with trial oversight.

The investigator must maintain source documents for each participant in the study, consisting of case and visit notes (hospital or clinic medical records) containing demographic and medical information, laboratory data, electrocardiograms, and the results of any other tests or assessments. All information on CRFs must be traceable to these source documents in the participant's file. The investigator must also keep the original informed consent form signed by the participant (a signed copy is given to the participant).

The investigator must give the monitor access to all relevant source documents to confirm their consistency with the data capture and/or data entry. Novartis monitoring standards require full verification for the presence of informed consent, adherence to the inclusion/exclusion criteria, documentation of SAEs, and of data that will be used for all primary variables. Additional checks of the consistency of the source data with the CRFs are performed according to the study-specific monitoring plan. No information in source documents about the identity of the participants will be disclosed.

# 12 Data analysis and statistical methods

The analysis will be conducted on all participants' data at the time the trial ends regardless of the interim analysis.

Any data analysis carried out independently by the investigator should be submitted to Novartis before publication or presentation.

# 12.1 Analysis sets

The following analysis sets will be used in this study.

Safety Set: The Safety Set includes all participants who received at least one dose of study treatment. The safety set will be used in the analysis of all safety variables.

Full Analysis Set (FAS): The FAS comprises all participants to whom study treatment has been assigned and received at least one dose of the treatment. The FAS will be used for all efficacy variables, unless otherwise stated.

Note that the Safety Set and the FAS are the same except that the Safety Set allows inclusion of participants to whom study treatment has not been assigned but received study drug in error.

## 12.2 Participant demographics and other baseline characteristics

Demographic and other baseline data including disease characteristics will be summarized descriptively for the Safety Set.

Categorical data will be presented as frequencies and percentages. For continuous data, mean, standard deviation, median, minimum, and maximum will be presented. For selected parameters, 25th and 75th percentiles will also be presented.

Relevant medical histories and current medical conditions at baseline will be summarized as frequencies and percentage combined by system organ class and preferred term for the Safety Set.

Baseline for safety is the last assessment (including unscheduled visits) obtained on or before the day of the first dose of study treatment. All assessments obtained after the first dose of study treatment are considered as post-baseline unless otherwise specified.

#### 12.3 Treatments

The Safety Set will be used for the analyses below.

Categorical data will be summarized as frequencies and percentages. For continuous data, mean, standard deviation, median, 25th and 75th percentiles, minimum, and maximum will be presented.

The duration of exposure in weeks to remibrutinib will be summarized.

The duration of exposure to study treatment will be computed without excluding temporary treatment interruptions.

Concomitant medications and significant non-drug therapies prior to and after the start of the study treatment will be summarized according to the ATC classification system.

Prior medications are defined as drugs taken and stopped prior to first dose of study medication. Any medication given at least once between the day of first dose of the study medication and the last day of study visit will be a concomitant medication, including those which were started pre-baseline and continued into the treatment period. Prior or concomitant medication will be identified based on recorded or imputed start and end dates of medication taking.

# 12.4 Analysis supporting primary objectives

This section will detail the statistical analysis of the primary (safety) estimand.

# 12.4.1 Definition of primary endpoints

The assessment of safety is based on all safety outcomes including reported adverse events or routine assessments such like vital signs, lab parameters or ECG measures. The estimand framework cannot be explicitly applied to all parameters. However, it may be useful to apply the estimand framework for treatment-emergent AEs.

In the majority of cases the assessments are not performed after permanent treatment discontinuation but the data collection are continued until end of safety follow-up period. For

the sake of consistency, main estimands defined for treatment-emergent AEs should follow the same logic.

The broad clinical question to be addressed is then: what is the safety of LOU064 while participant is still on-treatment, i.e., has not yet discontinued for any reasons?

The primary clinical question of interest regarding safety as primary endpoint is: What is the effect of remibrutinib treatment on the incidence of treatment-emergent adverse events (events started after the first dose of study medication or events present prior to start of treatment but increased in severity based on preferred term) in adult participants with CSU who are inadequately controlled by H1-antihistamine and receiving a stable locally label approved dose of a second-generation H1-antihistamine, regardless of treatment discontinuation for any reason, non-compliance (interruption) to treatment, switch of background medication or intake of a different second-generation H1-antihistamine as rescue medication/confounding prohibited medication? (see Section 2.1)

The primary (safety) endpoint (variable) is the number and the proportion of participants with treatment-emergent adverse event. The treatment-emergent adverse event is defined as event started during on-treatment period or event present prior to start of treatment but increased in severity based on preferred term. The on-treatment period lasts from the date of first administration of study treatment to 28 days after the date of the last actual administration of the study treatment.

# 12.4.2 Statistical model, hypothesis, and method of analysis

The number and the proportion (%) of participants with the treatment emergent adverse events will be summarized in the following ways:

- by primary system organ class and preferred term.
- by primary system organ class, preferred term and maximum severity.
- by Standardized MedDRA Query (SMQ) and preferred term.

Separate summaries will be provided for study medication related adverse events, death, serious adverse events, other significant adverse events leading to discontinuation.

In addition, a separate summary for deaths including on-treatment and post-treatment deaths will be provided.

The number and the proportion (%) of participants with adverse events of special interest for remibrutinib (related to identified and potential risks) will be summarized.

If a subject reported more than one adverse event with the same preferred term, the adverse event with the greatest severity will be presented. If a subject reported more than one adverse event within the same primary system organ class, the subject will be counted only once with the greatest severity at the system organ class level, where applicable.

All information obtained on adverse events will be displayed by participant.

All analyses for the primary (safety) endpoint will be performed descriptively. No statistical hypothesis is set for the primary (safety) endpoint in this study.

For all safety analyses, the Safety Set will be used.

# 12.4.3 Handling of intercurrent events of primary estimand

The analysis will account for different intercurrent events as explained in the following:

- Discontinuation of study treatment due to any reason: data collection will be maintained in the follow-up period. The data collected after these events will be used for analysis.
- Treatment non-compliance (interruption), switch of background medication, or intake of
  rescue medication as per protocol:
  ignore, i.e., data collection will be maintained and available measurements postintercurrent event will be used as if they had been obtained under the treatment. Data
  collected after these events will be used for analysis (Treatment policy strategy).
- Intake of strongly confounding prohibited medication (e.g., biologics treatment, cyclosporine, systemic corticosteroids): ignore, i.e., data collection will be maintained and available measurements post-intercurrent event will be used as if they had been obtained under the treatment: Data collected after these events will be used for analysis (Treatment policy strategy).
- Administration of medications affecting the evaluation of potential risks, including: (a) anticoagulant/anti-platelet medications (other than acetylsalicylic acid up to 100 mg/d or clopidogrel); (b) live attenuated vaccines; (c) strong CYP3A4 inhibitors; (d) moderate/strong CYP3A4 inducers, (e) Oral BCRP\* substrates that may have increased exposure when co-administered with remibrutinib (pitavastatin, rosuvastatin, sulfasalazine and ubrogepan): ignore, i.e., data collection will be maintained and available measurements post-intercurrent event will be used as if they had been obtained under the treatment: Data collected after these events will be used for analysis (Treatment policy strategy).
- Intake of other prohibited medication: ignore, i.e., data collection will be maintained and available measurements post-intercurrent event will be used as if they had been obtained under the treatment: Data collected after these events will be used for analysis (Treatment policy strategy).
- \* Assessment of confounder BCRP will be specified in the SAP.

#### 12.4.4 Handling of missing values not related to intercurrent event

No imputation will be done for missing data. All available data will be used for the analyses.

# 12.4.5 Sensitivity analyses

If unexpectedly high incidence of adverse events of special interest (AESI) is observed, then sensitivity analysis may be performed for the AESI.

The following sensitivity analysis may be performed on AESI, to assess the causality between the occurrence of AESI and medications. The sensitivity analysis will be implemented with the same target population, on AESI variable and the summary measure as for the primary estimand, but using the different assumptions or handling of intercurrent events.

- Intake of strongly confounding prohibited medication (e.g., biologics treatment, cyclosporine, systemic corticosteroids): only measurements prior to intake of these prohibited medications will be used for analysis (While on treatment strategy).
- Intake of medications affecting the evaluation of potential risks, including: (a) anticoagulant/anti-platelet medications (other than acetylsalicylic acid up to 100 mg/d or clopidogrel); (b) live attenuated vaccines; (c) strong CYP3A4 inhibitors; (d) moderate/strong CYP3A4 inducers, (e) Oral BCRP\* substrates that may have increased exposure when co-administered with remibrutinib (pitavastatin, rosuvastatin, sulfasalazine and ubrogepan): only measurements prior to intake of these medications will be used for analysis (While on treatment strategy).
- \* Assessment of confounder BCRP will be specified in the SAP.

## 12.4.6 Supplementary analysis

No supplementary analysis is planned for the primary (safety) endpoints.

# 12.5 Analysis supporting secondary objectives

This section will detail the statistical analysis of the secondary (efficacy) estimands (see Section 2.2).

# 12.5.1 Efficacy and/or Pharmacodynamic endpoints

#### **Definition of secondary endpoints**

The secondary clinical question of interest regarding efficacy as secondary endpoint, change from baseline in UAS7 score at Week 12 is: What is the effect of remibrutinib treatment on the change from baseline in UAS7 score at Week 12 after treatment in adult participants with CSU who are inadequately controlled by H1-antihistamine and receiving a stable locally label approved dose of a second-generation H1-antihistamine, regardless of treatment discontinuation for any reason or intake of a different second-generation H1-antihistamine as rescue medication and considering strongly confounding prohibited medication use as an unfavorable outcome?

One of the secondary (efficacy) endpoints (variables) is the absolute change from baseline in UAS7 score at Week 12, which is the UAS7 score at Week 12 minus the UAS7 score at baseline. The UAS7 is the sum of the HSS7 score and the ISS7 score, and ranges from 0-42. Weekly scores (HSS7 and ISS7 scores) will be derived by adding up the average daily scores of the 7 days preceding the visit.

Other secondary endpoints are listed in the Table 2-1.

#### Statistical model, hypothesis, and method of analysis

The secondary (efficacy) variables during the study, including absolute change from baseline in UAS7 score at Week 12, will be summarized (by visit, if applicable).

Baseline for efficacy is comprised of the 7 days prior to Day 1 (Enrollment in treatment period day) for UAS7 and other assessment on or prior enrollment in treatment period day.

All analyses for the secondary (efficacy) endpoints will be performed descriptively. No statistical hypothesis is set for the secondary (efficacy) endpoints in this study.

For all efficacy analyses, the FAS will be used.

The analyses will be performed based on the data after the missing data imputation for the intercurrent events have been performed.

#### Handling of intercurrent events of secondary estimand

Participants who discontinue from study treatment early due to any reason will be encouraged to stay in the study following the procedures. Every effort will be made to continue to follow participants who discontinued from study treatment up to Week 12. These are considered as Retrieved drop-out (RDO) participants.

The analysis will account for different intercurrent events as explained in the following:

- Discontinuation of study treatment prior to Week 12 due to any reason: ignore, i.e., data collection will be maintained and available measurements post-treatment discontinuation will be used as if they had been obtained under the treatment: RDO data collected after study treatment discontinuation will be used for analysis (Treatment policy strategy).
- Treatment non-compliance (interruption), switch of background medication, or intake of rescue medication as per protocol prior to Week 12: ignore, i.e., data collected after these events will be used for analysis (Treatment policy strategy). Intake of strongly confounding prohibited medication (e.g., biologics treatment at any time before Week 12, cyclosporine after Week 8, systemic corticosteroids after Week 8): measurements after this event will be excluded from the analysis and will be imputed using the worst value of the endpoint (e.g., 42 for UAS7 score at Week 12, or non-response for binary endpoints) (Composite strategy (irrespective of potential occurrence of other intercurrent events)).
- Intake of other prohibited medication prior to Week 12: ignore, i.e., data collected after these events will be used for analysis (Treatment policy strategy).

#### Handling of missing values not related to intercurrent event

The UAS7 score is derived from the sum of the HSS7 score and the ISS7 score. The HSS7 and ISS7 score will be derived by adding up the daily HSS and ISS scores of the 7 days preceding the visit, respectively. The daily score (HSS and ISS) will be calculated by averaging the morning and evening HSS and ISS score, respectively. If one of the morning or evening scores is missing, the non-missing score for that day (morning or evening) will then be used as the daily score.

For each weekly score from the UPDD (i.e., HSS7, ISS7), if one or more of the daily scores are missing, the following principles will be applied to handle the missing data:

- The weekly UAS7 is the sum of both the HSS7 score and the ISS7 score and will be missing if at least one of them is missing.
- If a patient has at least 4 non-missing daily (morning or evening) scores within the 7 days prior to the study visit, the weekly score for HSS or ISS will be calculated as the sum of the available eDiary scores of that week, divided by the number of non-missing days, multiplied by 7.

Amended Protocol Version No. 01 (Clean)

 If there are less than 4 non-missing daily scores within the prior 7 days, then the weekly score for HSS or ISS will be considered as missing for that week. Accordingly, no UAS7 can be calculated.

If there is any intermittent missing data not due to any of the intercurrent events as we defined above, the missing data will be handled without imputation and all available data will be used for the analysis.

#### Sensitivity analyses

No sensitivity analysis is planned for the secondary (efficacy) estimands.

#### Supplementary analyses

No supplementary analysis is planned for the secondary (efficacy) estimands.

### 12.5.2 Safety endpoints

Safety summaries (tables, figures) include only data from the on-treatment period with the exception of baseline data which will also be summarized where appropriate (e.g., change from baseline summaries).

#### Adverse events

See the Section 12.4.

### Vital signs

All vital signs data will be listed by participant, and visit/time and if ranges are available, abnormalities (and relevant orthostatic changes) will be flagged. Summary statistics will be provided by visit.

#### 12-lead ECG

PR, QRS, QT, QTcF, and RR intervals will be obtained from 12-lead ECGs for each participant during the study. ECG data will be read and interpreted centrally.

All ECG data will be listed by participant and visit/time, abnormalities will be flagged. Summary statistics will be provided by visit/time.

# Clinical laboratory evaluations

All laboratory data will be listed by participant and visit and if normal ranges are available abnormalities will be flagged. Summary statistics for the change from baseline will be provided by visit. Shift tables using the low/normal/high/ (low and high) classification will be used to compare baseline to the worst on-treatment value.

### Dermatology Life Quality Index (DLQI)

An overall score will be calculated according to the scoring manual.

For DLQI total score, summary statistics will be provided for absolute change from baseline as well as for percent change from baseline by visit.

The proportion of participants achieving DLQI = 0-1 will be provided by visit.

## Angioedema Activity Score (AAS)

For AAS7 score, summary statistics will be provided for absolute change from baseline as well as for percent change from baseline over time, in participants with angioedema at baseline (AAS7 >0) and in all participants.

The proportion of participants achieving AAS7 = 0 will be provided over time.

The cumulative number of weeks achieving AAS7 = 0 response between baseline and Week 12 will be derived based on the AAS eDiary and UPDD diary. A weekly AAS7 score will be derived by adding up the daily scores of the 7 days preceding the visit, and ranges from 0 to 105. If the AAS7 assessment is missing, it will be considered as a non-response for the cumulative number of weeks that participants achieve AAS7 = 0 response calculation.

For angioedema burdened days, summary statistics will be provided for absolute change from baseline as well as for percent change from baseline over time.

	_	
2		

## 12.7 Interim analyses

An interim analysis may be conducted when all participants have completed their Week 24 visit or discontinued early. The interim analysis at the time of this Week 24 database lock would be utilized for the purpose of submission to health authorities for marketing authorization approval. Timing of this interim analysis may be changed from Week 24 depending on the time of the submission, and will be documented in the SAP.

Additional interim analyses may be conducted at the discretion of the Sponsor to support decision making concerning the current clinical study, the sponsor's clinical development projects in general, or in case of any safety concerns.

The decision to conduct optional interim analyses and the timing/data to be reviewed will be documented in the SAP prior to the conduct of any interim analysis.

# 12.8 Sample size calculation

Since CSU is a chronic disease, and remibrutinib is expected to be administered over a long period, safety in long-term treatment needs to be confirmed. "Regarding sample size and treatment period required to assess safety at the clinical study stage of a new drug anticipated to be administered for a non-fatal disease over a long period" (Notification No. 592 of the Pharmaceuticals and Cosmetics Division, Pharmaceutical Affairs Bureau, MHLW, dated 24-May-1995), this notification requires to collect safety data of at least 100 Japanese patients who receive the drug over one year. CLOU064A2201E1 study was planned to collect efficacy and safety data of about 33 Japanese CSU participants exposed to remibrutinib greater than or equal to the application dose for one year and CLOU064A2301 study was planned to collect efficacy and safety data of about 15 Japanese CSU participants exposed to remibrutinib of the application dose for one year. Therefore this study, CLOU064A1301, is designed to obtain safety data of approximately 70 Japanese CSU participants exposed to remibrutinib at the application dose for one year. Since approximately 30% screening failure rate and approximately 15% dropout rate are expected, approximately 100 patients will need to be

screened in order to collect approximately 70 participants who enter the treatment period and to collect a total of approximately 60 completed participants.

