# 5 Study Population

The study population will consist of approximately 70 eligible female and male adult participants with CSU inadequately controlled by second generation H1-antihistamines (at least at local label approved dose).

The screen failure rate is estimated to be 30%, meaning approximately 100 participants are expected to be screened.

Participants who drop out after they have entered into the treatment period will not be replaced.

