#### 14.1 Protocol amendments

Any change or addition to the protocol can only be made in a written protocol amendment that must be approved by Novartis, health authorities where required, and the IRB/IEC prior to implementation.

Notwithstanding the need for approval of formal protocol amendments, the investigator is expected to take any immediate action required for the safety of any participant included in this study, even if this action represents a deviation from the protocol. In such cases, Novartis should be notified of this action and the IRB/IEC at the study site should be informed according to local regulations.

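### Protocol 12.8 and SAP 3 label about 70 as exposed for one year, but 70 is the number entering treatment; on the stated dropout about 60 are expected to complete 52 weeks

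*Protocol*

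**What the plan says.** Protocol 12.8 starts from a Japanese notification on long-term safety data: "this notification requires to collect safety data of at least 100 Japanese patients who receive the drug over one year". It then gives the planned contributions of two other studies. CLOU064A2201E1 is to supply "about 33 Japanese CSU participants exposed to remibrutinib greater than or equal to the application dose for one year", and CLOU064A2301 "about 15 Japanese CSU participants exposed to remibrutinib of the application dose for one year". From these it concludes that the present study "is designed to obtain safety data of approximately 70 Japanese CSU participants exposed to remibrutinib at the application dose for one year".

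The next sentence assumes about 30% screen failure and about 15% dropout, and says that about 100 patients must be "screened in order to collect approximately 70 participants who enter the treatment period and to collect a total of approximately 60 completed participants". SAP 3 carries the same two sentences.

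Elsewhere 70 is a headcount at the start of treatment. Protocol 5 says "The study population will consist of approximately 70 eligible female and male adult participants" and adds that "Participants who drop out after they have entered into the treatment period will not be replaced". SAP 1.1 likewise gives about 70 as the number enrolled into the treatment period. Protocol 6.1.4 sets the planned treatment duration at 52 weeks.

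**The concern.** The same number carries two labels that cannot both hold. If about 70 enter, 15% drop out and none is replaced, then about 70 cannot also be the number expected to have a year of exposure.

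The label matters because nothing else sizes the study. Protocol 12.4.2 and 12.5.1 set no hypothesis, and Protocol 12.8.1 and 12.8.2 mark endpoint-based sample size as not applicable. The count of one-year exposures is the whole sizing argument. The sentence that draws the conclusion from the requirement of 100 uses 70, and the 60 is never set against the 100. A reader who follows the reasoning as written adds 70 to the other two studies and sees a larger margin than the plan's own dropout rate supports.

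**Working it through.** **Inputs.** About 100 screened, 30% screen failure, 15% dropout, 33 and 15 from the other two studies, and a requirement of 100 (all Protocol 12.8 and SAP 3). No replacement of dropouts (Protocol 5). Treatment of 52 weeks (Protocol 6.1.4). Completing 52 weeks is taken as about one year of exposure.

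**The plan's own chain.**
- Entering: 100 x (1 - 0.30) = 70. This matches the stated 70.
- Completing: 70 x (1 - 0.15) = 59.5. This matches the stated figure of about 60.

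**The one-year label.**
- Stated as exposed for one year: 70. Expected: 59.5.
- Difference: 70 - 59.5 = 10.5, and 10.5 / 59.5 = 17.6%.
- Had 70 at one year been the aim, 70 / 0.85 = 82.4, so 83 would have to enter, and 83 / 0.70 = 118.6, so about 119 would have to be screened. Neither document plans that, which supports reading 70 as the entry number.

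**Against the requirement of 100, with 33 and 15 as one-year counts (as worded).**
- Other studies: 33 + 15 = 48, so 100 - 48 = 52 are needed from this study.
- Using 70: 48 + 70 = 118, an apparent margin of 18.
- Using 59.5: 48 + 59.5 = 107.5, about 108, a margin of 7.5.
- With independent dropout at 15%, the binomial probability that at least 52 of 70 complete is 0.994.

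**The same, with 33 and 15 as entry numbers and the same 15% loss (an assumption).**
- Other studies: 48 x 0.85 = 40.8.
- Total: 40.8 + 59.5 = 100.3, a margin of 0.3.

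Whichever applies to the other two studies, using 70 in place of 59.5 raises the apparent total by 10.5.

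**The case against.** The best defence is that nothing is hidden. The dropout rate, the 70 entering and the 60 completing stand in the very next sentence, and the sizing argument ends at 60. The disputed sentence can also be read as planned exposure, meaning 70 people put on a one-year regimen; Protocol 4.1 uses similar design language. Actual exposure will be tabulated from the final data, SAP Amendment 4 is already dated just before the final database lock, and no decision turns on the label.

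Most of this stands, and it is why the weight is low. The planned-exposure reading does not remove the conflict, though. The requirement concerns patients who actually receive the drug for a year, and the disputed sentence is offered as the answer to it. The 33 and 15 carry the same phrase, so if it means intended duration, none of the three counts is a one-year count and the paragraph does not show that 100 is reached.

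Three stronger inferences are tempting, and the documents do not support them.
- *The study is too small.* On the figures as worded, 52 are needed and about 60 are expected.
- *The pooled total is simply 108.* That depends on 33 and 15 being true one-year counts, which neither document settles.
- *The exposure table's category of at least 52 weeks will hold about 60.* SAP 2.4.1 counts exposure from first to last dose, so that category needs 52 x 7 = 364 days. Protocol 8 lets visits fall as close to the scheduled day as possible, so a completer seen somewhat early can land in the category below. Completing is not the same as 364 days of dosing.

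**Conclusion.** The point holds as a mislabelled figure. Protocol 12.8 and SAP 3 attach one year of exposure to the number entering treatment, which is 10.5 participants (17.6%) above the count the plan itself expects to complete. The attrition arithmetic is right, the figure of about 60 is disclosed, and the requirement of 100 is met on the numbers as worded, with a margin of 7.5 rather than the apparent 18.

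This rests on the stated 15% dropout, on no replacement, and on treating 52 completed weeks as about one year. The size of the pooled margin also depends on what 33 and 15 represent: it falls to 0.3 if they are entry numbers subject to the same 15% loss. That is a reason to ask the sponsor, not evidence of a shortfall. Severity is low.

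**What to change.** In Protocol 12.8 and SAP 3, reword the disputed sentence along these lines: *approximately 70 participants entering treatment, of whom approximately 60 are expected to complete 52 weeks (about one year) of treatment*. Set the 60, not the 70, against the requirement of 100.

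Before any pooled total is written in, the sponsor should confirm whether 33 and 15 are one-year exposed counts or entry numbers. If they are one-year counts, the total is about 108. If they are entry numbers and the same 15% loss is assumed, it is about 100. Until that is confirmed, give the total conditionally or leave it out.

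The cost is one sentence in each of two documents and a less favourable stated figure. The SAP sentence can change at its next version. For the protocol, "Any change or addition to the protocol can only be made in a written protocol amendment", with the approvals listed in section 14.1, so the correction can be carried in the next amendment. No extra participants are needed, and conduct and analysis do not change.
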